4.1.3.2 Physical Functioning Assessments

4.1.3.2.1 Range of Motion

All participants with a target PN that causes motor dysfunction or weakness at baseline will undergo a focused evaluation of range of motion of the affected joints during the Treatment Phase, in accordance with the SoA (Sections 1.3-1.4 of the protocol). For each participant, range of motion results will be summed and this will be taken as an overall score for each visit.

4.1.3.2.2 Strength Assessments

All participants with a target PN that causes motor dysfunction or weakness at baseline will undergo a focused evaluation of strength of the affected muscle groups in accordance with the SoA (Sections 1.3-1.4 of the protocol) and will be included for this analysis. Strength will be assessed utilizing a Sponsor provided dynamometer and Medical Research Council (MRC) Muscle Scale. The MRC grading assessment should be conducted prior to the dynamometer assessment. Dynamometer assessment and MRC grading (0-5/5) must be conducted in accordance with the study reference manual. For each participant, the sum of the scores for the muscle groups tested will be taken as an overall score for each visit.

Document: S:\Q_146\Q_03974\MEK-NF-201\Prog_Stat\Documentation\SAP\MEK-NF-201 SAP v1.0.0.docx
Author:

4.1.3.2.3 6-Minute Walk Test

Participants with a target PN that causes airway or lower extremity motor dysfunction at baseline will undergo a 6-minute walk test in accordance with the SoA (Sections 1.3-1.4 of the protocol) that will be included for this analysis. Additionally, pulse rate, systolic blood pressure and diastolic blood pressure will be collected following a 5-minute rest after the 6-minute walk test is completed.

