8.1.3. Strength Assessment

All participants with a target PN that causes motor dysfunction or weakness will undergo a focused evaluation of strength of the affected muscle groups in accordance with the SoA (Section 1.3) during the Treatment Phase. The contralateral side will be tested for comparison. This evaluation should be performed by Rehabilitation Medicine, Physiatry, or Physical Therapy, if possible, and should ideally be completed by the same examiner at each visit, if feasible.

Strength should be assessed utilizing a Sponsor provided dynamometer and Medical Research Council (MRC) Muscle Scale. The MRC grading assessment should be conducted prior to the dynamometer assessment. Dynamometer assessment and MRC grading (0-5/5) must be conducted in accordance with the study reference manual.

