5.5 Handling of Missing Data

Missing data will only be imputed in the following cases:

Document: S:\Q_146\Q_03974\MEK-NF-201\Prog_Stat\Documentation\SAP\MEK-NF-201 SAP v1.0.0.docx

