6.11.3.2 Change in Functional Impairments

Change from baseline in functional impairments, measured according to Section 4.1.3.2, will be summarized by visit and age cohort.

In participants who have tumors that affect functional status at baseline, the change from baseline in muscle strength and range of motion in the PN affected areas, as described in Section 4.1.3.2, will be presented by visit.

In addition, for all physical functioning assessments, plots will be created for scores at each visit. This will be presented individually for each participant, as well as all being included in a whole population plot.

All recorded functional impairment data of any form will be listed.

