6.11.3.2.1 Strength

For each of the individual strength assessments, to assess the change from baseline at a visit, a participant will need assessments in which all the following categories, as assessed at baseline, match at that visit:

- Side affected
- Position during assessment (sitting/supine/lateral decubitus)
- Muscle group assessed

Assessment of strength will be conducted only in the area affected by the target tumor. Measurements will be obtained using Medical Research Council (MRC) grading followed by quantitative assessments using the sponsor provided MicroFET2 dynamometer.

The MRC grading will be presented by each affected area summarizing the number and percent of participants in each category below:

Document: S:\Q_146\Q_03974\MEK-NF-201\Prog_Stat\Documentation\SAP\MEK-NF-201 SAP v1.0.0.docx
Author:

0 – No movement is observed.

- 1 Only a trace or flicker of movement is seen or felt in the muscle or fasciculations are observed in the muscle.
- 2 Muscle can move only if the resistance of gravity is removed. As an example, the elbow can be fully flexed only if the arm is maintained in a horizontal plane.
- 3 Muscle strength is further reduced such that the joint can be moved only against gravity with the examiner's resistance completely removed. As an example, the elbow can be moved from full extension to full flexion starting with the arm hanging down at the side.
- 4 Muscle strength is reduced but muscle contraction can still move joint against resistance.
- 5 Muscle contracts normally against full resistance.

The strength measured by the dynamometer by each area location will be summarized and the percent change from baseline using standard summary statistics will be summarized by age cohort and by visit.

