6.11.3.2.2 Range of Motion

For the range of motion assessments, to assess the change from baseline at a visit, a participant will need assessments in which all three categories, as assessed at baseline, match at that visit:

- Joint assessed
- Motion tested
- Type (passive/active)

The range of motion for that location will be summarized and the percent change using standard summary statistics will be summarized by age cohort and by visit.

6.11.3.2.3 6-Minute Walk Test

Participants with a target PN causing airway or lower extremity motor dysfunction at baseline will be assessed for change in 6-minute walk test distance. Vital signs are performed prior to the start of the walk test. The object of this test is to walk as far as possible over 6 minutes. After completing the test, participant will be instructed to rest for 5 minutes, after which time vital signs are repeated. The total meters walked will be captured. Standard summary statistics of length walked and the pre-/post vitals will be summarized by each visit.

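### The exploratory overall strength and range-of-motion scores are sums over whatever was tested at each visit, so a change in the set of items tested can pass for a change in function

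*SAP*

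**What the plan says.** **How the scores are built.** SAP Section 4.1.3.2.2 defines the strength score for each participant: "the sum of the scores for the muscle groups tested will be taken as an overall score for each visit". Section 4.1.3.2.1 does the same for joints: "range of motion results will be summed and this will be taken as an overall score for each visit". Neither section names a fixed set of items, a minimum number, or a rule for an item that was not tested.

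**How they are used.** SAP Section 6.11.3.2 states: "Change from baseline in functional impairments, measured according to Section 4.1.3.2, will be summarized by visit and age cohort". It also calls for plots of scores at each visit, for each participant and for the whole population.

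**Matching rules.** Section 6.11.3.2.1 introduces its rule with these words: "For each of the individual strength assessments, to assess the change from baseline at a visit". Side affected, position and muscle group must agree with baseline. Section 6.11.3.2.2 says that "a participant will need assessments in which all three categories, as assessed at baseline, match at that visit"; its categories are joint, motion, and passive or active type. Side is not among them.

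**Missing data.** SAP Section 5.5 opens: "Missing data will only be imputed in the following cases". The cases that follow do not include the functional assessments.

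**The other side of the body.** Protocol Section 8.1.3 says of strength testing: "The contralateral side will be tested for comparison". Protocol Section 8.1.5 has the same provision for range of motion. SAP Section 6.11.3.2.1 says: "Assessment of strength will be conducted only in the area affected by the target tumor".

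**The concern.** A sum has a stable meaning only if the same items enter it each time. Here the number of terms is whatever the examiner tested that day. If a muscle group or joint is skipped at a later visit, the sum loses that item's whole value, which is usually much larger than any plausible treatment-related change in the items that remain. If an item is tested for the first time after baseline, the sum gains its whole value.

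The SAP deals with incomplete items for its other instruments. PedsQL, NRS-11 and PII each have a threshold for missing items or days, PROMIS requires every item, and P-OMAQ uses the mean of the answered questions. The two functional sums have no such rule. The existence of matching rules also suggests that the authors expected the tested items to differ between visits.

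At stake are the mean change by visit and cohort in the overall scores, and the participant and population plots. A participant whose tested muscles all improved could be shown as declining, and two programmers could build different scores from the same records.

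**Working it through.** The documents give no figure for these scores, so there is nothing to reproduce. The check is arithmetic on **assumed** scores. From the documents it uses only the MRC grade range of 0 to 5 per muscle group and the summing rule.

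**Formulas.**
- Change in the plain sum = (sum of items tested at the visit) − (sum of items tested at baseline).
- Matched change = sum, over items tested on both occasions, of (visit value − baseline value).

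**1. No true change, one item untested later.** Assume k muscle groups, all at grade 4 throughout, with one untested at follow-up. The plain sum goes from 4k to 4(k−1), a change of −4 whatever k is. The matched change is 0.

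| k | Baseline | Follow-up | Change | Percent |
|---|---|---|---|---|
| 2 | 8 | 4 | −4 | −50.0% |
| 3 | 12 | 8 | −4 | −33.3% |
| 4 | 16 | 12 | −4 | −25.0% |
| 6 | 24 | 20 | −4 | −16.7% |
| 8 | 32 | 28 | −4 | −12.5% |

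For range of motion, assume joints at 90 and 120 degrees with the 120-degree joint untested later. The sum goes from 210 to 90, and −120/210 = −57.1%, with no change in either joint.

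**2. No true change, one item added later.** Three groups at grade 4 give 12 at baseline. If a fourth group, also at grade 4, is tested at the visit, the sum is 16, a change of +4. The matched change is 0.

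**3. Real gain, one item untested.** Assume k groups at grade 4; k−1 of them rise to 5 and the last is not tested. The plain change is 5(k−1) − 4k = k − 5, and the matched change is k − 1.
- k = 4: 16 to 15, change −1; matched change +3. The sign is reversed.
- k = 5: 20 to 20, change 0; matched change +4. The gain vanishes.
- k = 6: 24 to 25, change +1; matched change +5. Most of the gain is lost.

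**4. Effect of a stable contralateral side, if it were in the sum.** Assume affected grade 3 rising to 4 beside a constant 5.
- Affected side alone: change +1, and 1/3 = 33.3%.
- Both sides: 8 to 9, change still +1, and 1/8 = 12.5%.

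For range of motion, assume 90 rising to 108 degrees beside a constant 140.
- Affected side alone: change +18, and 18/90 = 20%.
- Both sides: 230 to 248, change still +18, and 18/230 = 7.8%.

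A stable other side cancels from the absolute change. It reduces only percent change, which the SAP summarizes by area or location and not on the sum.

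**The case against.** **The matching rules may already cover the sum.** They sit in subsections of Section 6.11.3.2, the section that calls for change from baseline, so they can be read as saying how every such change is computed. The range-of-motion rule, unlike the strength rule, is not confined to individual assessments. This has some force, and it makes the problem one of unstated scope more than outright error. But neither subsection says that unmatched items leave the sum, and the strength rule is worded for single assessments.

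**The direction of any bias is unknown.** A reader might infer that missing items push the scores down over time. The documents do not support that as a general claim. They give no rate of partly completed examinations. A wholly missed visit yields no score instead of a low one, and items added after baseline move the sum up. Testing procedures are in the study reference manual, which was not available to check. This objection stands.

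**The contralateral side.** A reader might also infer that the unaffected side enters the sum and shrinks the treatment effect. The documents do not support this. The SAP refers to affected muscle groups, affected joints and PN-affected areas, restricts strength testing to the tumor-affected area, and the protocol tests the other side only as a comparator. If a stable other side did enter, the absolute change would be the same (step 4). What remains is narrower: no sentence expressly keeps contralateral results out of the sum, and the gap is wider for range of motion because side is not a matching category.

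**Little rests on these scores.** They are exploratory, and no test, model or decision rule uses them. The detailed outputs are by area or location, participants are plotted individually, and all functional data are listed, so a dropped item could be traced. This is correct and limits the importance of the point.

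**Conclusion.** The point holds for the overall summed scores only. Both are unweighted sums with no completeness rule, and the matching rules that protect the individual and by-location analyses are not stated to extend to them. One untested item can reverse the sign of change (−1 against a matched +3 with four muscle groups). Where nothing has changed, it can move the score by an item's full value: 4 MRC points, or 12.5% to 50% of the baseline sum with eight down to two groups, in either direction.

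These sizes rest on assumed scores and show what the rule permits, not what will happen. How often it matters depends on how often the tested set differs between visits, which the documents do not report. Neither a systematic downward bias nor dilution by the unaffected side is established. The primary endpoint, the sample size and the secondary endpoints are unaffected. This is a minor clarification worth making because it is cheap.

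**What to change.** Amend SAP Sections 4.1.3.2.1, 4.1.3.2.2 and 6.11.3.2 as follows:

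- For each visit, compute change in the overall score as the sum (or mean) over items assessed at both baseline and that visit under the same matching categories: side, position and muscle group for strength; joint, motion and type for range of motion, **with side added**.
- Set the change to missing if no items match.
- State that contralateral results, which the protocol collects for comparison, are not part of the score.
- Apply the same rule to the by-visit plots of the overall score.

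Either form removes the artefact. The mean has the advantage that its scale does not depend on how many items matched: in the four-group example the matched sum is +3 over three items and the mean is +3/3 = +1 grade per muscle group.

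The cost is SAP wording and programming, with no new data collection. The downside is that visits with no matched item drop out, and the score at different visits may rest on different subsets of a participant's baseline items.

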4.1.3.3 Patient Global Impression of Severity

The patient global impression of severity (PGIS) is a single item scale that evaluates the participant's perception of the overall severity of their NF1-related symptoms over the past week on a 4-point scale ranging from "none" to "severe." The PGIS has a 7-day recall period and is completed by participants ≥ 6 years of age. The scale is presented in Appendix 1.1.

The PGIS is assessed at the time points specified in the SoA (Section 1.3 of the protocol).

4.1.3.4 Patient Global Impression of Change

The patient global impression of change (PGIC) is a single item scale that evaluates the participant's perception of the overall change in their overall status since the start of the study treatment on a 7-point scale ranging from "very much better" to "very much worse." The PGIC will be completed by participants ≥ 6 years of age during the Treatment Phase. The scale is presented in Appendix 1.2.

The PGIC is assessed at the time points specified in the SoA (Section 1.3 of the protocol).

4.1.3.5 Target Tumor Biopsy

See Section 4.3.8.

4.1.3.6 Time to Progression

Time to progression (TTP) is defined as the time in months between the start of treatment to the first date of radiographic disease progression as measured by MRI. TTP will be summarized in months as follows: (date of event (i.e., radiographic disease progression) or censoring – treatment start date + 1) / 365.25 *12. Participants without radiographic disease progression will have their results censored at the last adequate tumor assessment date. Participants who lack any tumor response data post baseline will have their event time censored at treatment start date.

If participants receive any surgery impacting the target PN or start subsequent systemic therapy for the treatment of PNs prior to radiographic progression, then the participant's event time will be censored at the last adequate tumor assessment date prior to surgery or subsequent PN treatment. The rules for censoring and events for TTP are summarized in Table 6.

TTP will be analyzed for the FAS and also a subset of participants in the FAS who have progressive disease at baseline.

Table 6: Censoring and Event Rules for TTP

Situation	Date of Censoring or Event	Outcome
No adequate tumor assessment post baseline	Treatment start date	Censored

Document: S:\Q_146\Q_03974\MEK-NF-201\Prog_Stat\Documentation\SAP\MEK-NF-201 SAP v1.0.0.docx

Author:

Situation	Date of Censoring or Event	Outcome
No radiographic disease progression	Date of last adequate tumor assessment	Censored
Two or more consecutive missing or non- adequate tumor assessments	Date of last adequate tumor assessment before the first missing or non-adequate assessment	Censored
Death before radiographic progression	Date of last adequate tumor assessment	Censored
New surgery or subsequent anticancer PN therapy started prior to radiographic disease progression	Date of last adequate tumor assessment before the start of new therapy or surgery	Censored
Radiographic disease progression that has been verified by BICR	Date of the earliest tumor assessment that results in a finding of progression	Event

4.1.3.6.1 Sensitivity Analysis of Time to Progression

The following sensitivity analyses using the REiNS criteria (Dombi, 2013) will be performed using the target PN volume from the two central readers, separately:

- TTP using all scans; defined as the time from start of treatment to the derived disease progression using BICR PN volume data considering all MRI scans.
- TTP using real-time review, defined as the time from start of treatment to the derived disease progression using BICR PN volume data considering only the scans up to and including each visit, in order to assess PD in a real-time review.

The censoring rules for the sensitivity analyses will be the same as for the main TTP analysis and will follow Table 6.

4.1.3.7 Progression Free Survival

Progression free survival (PFS) is defined as the time from treatment start date to the first occurrence of radiographic disease progression or death, whichever occurs first. PFS will be summarized in months as follows: (date of event (i.e. radiographic progression or death) or censoring – treatment start date + 1) / 365.25 *12. Any participant who does not experience radiographic disease progression or death while on study will have their results censored to their last adequate tumor assessment date. Participants who lack any tumor response data post-baseline will have their event time censored at treatment start date.

If participants receive any surgery impacting the target PN or start subsequent systemic therapy for the treatment of PNs prior to radiographic progression, then the participant is censored at the last adequate tumor assessment date prior to target PN surgery or subsequent systemic PN treatment. The rules for censoring and events for PFS are summarized in Table 7.

Document: S:\Q_146\Q_03974\MEK-NF-201\Prog_Stat\Documentation\SAP\MEK-NF-201 SAP v1.0.0.docx

Author:

PFS will be analyzed for the FAS and also a subset of participants in the FAS who have progressive disease at baseline.

Table 7: Censoring and Event rules for PFS

Situation	Date of Censoring or Event	Outcome
No adequate tumor assessment post baseline	Treatment start date	Censored
No radiographic disease progression or death	Date of last adequate tumor assessment	Censored
New surgery or subsequent anticancer PN therapy started prior to radiographic disease progression	Date of last adequate tumor assessment before the start of new therapy or surgery	Censored
Two or more consecutive missing or non- adequate tumor assessments	Date of last adequate tumor assessment before the first missing or non-adequate assessment	Censored
Radiographic disease progression that has been verified by BICR	Date of the earliest tumor assessment that results in a finding of progression	Event
Death before radiographic disease progression	Date of death	Event

4.1.3.7.1 Sensitivity Analysis of Progression Free Survival

The following two types of sensitivity analyses using the REiNS criteria (Dombi, 2013) will be performed using the target PN volume from the two central readers, separately.

- PFS applying REiNS using all scans; defined as the time from start of treatment to the derived disease progression using BICR PN volume data considering all the MRI scans.
- PFS applying REiNS using real-time review, defined as the time from start of treatment to the derived disease progression using BICR PN volume data considering only the scans up to and including each visit, in order to assess PD in a real-time review.

The censoring rules for the sensitivity analyses will be the same as for the main PFS analysis and will follow Table 7.

4.1.3.8 Historical Controls

Full details on the analyses performed using historical control data (NCI 01-C-0222 and NCI 08-C-0079) will be summarized separately in an addendum to this SAP.

Document: S:\Q_146\Q_03974\MEK-NF-201\Prog_Stat\Documentation\SAP\MEK-NF-201 SAP v1.0.0.docx

Author:

Protocol Number: MEK-NF-201

4.1.3.9 Pediatric Oral Medicine Acceptability Questionnaire (P-OMAQ)

The P-OMAQ is a clinical outcome assessment conducted as a self-report by pediatric participants (P-OMAQ-P), with an associated adult caregiver observer report (P-OMAQ-C) assessing the acceptability of the dispersible tablet (pediatric) dosage formulation. The P-OMAQ-P is a 12-item PRO for respondents of ≥ 8 years of age. The P-OMAQ-C is a 19-item PRO for adult caregivers (aged ≥18 years) overseeing study drug dosing of pediatric participants aged 2 to 17 years.

Each questionnaire is provided with a "past 7 days" recall with all items using a 5-point Numerical Rate Scale with higher item-scores reflecting greater oral treatment acceptability. The overall P-OMAQ-P and P-OMAQ-C scores for a participant in the study will be taken as the mean of all answered questions on the respective questionnaire.

The P-OMAQ will only be assessed once per participant in the study taking the tablet. This assessment can take place at any of the time points specified in the SoA (Sections 1.3-1.4 of the protocol).

4.1.3.10 Tumor Volume

Tumor volume (mL) will be measured independently by two blinded independent central reviewers, as described in Section 4.1.1. Unscheduled visits may be mapped to a visit window based on the criteria in Section 5.6.

The volume measured at the screening (SCR Volume) visit will be taken as the baseline for calculation of confirmed objective response rate, with percentage change from baseline at Cycle X (CX) calculated as:

((CX Volume - SCR Volume)/SCR Volume)*100.

The above calculation will be done for the average of the volumes recorded by each reviewer, unless there was a response adjudication in which the adjudicated reviewer's volume will be selected. In addition, this calculation will be done for each reviewer separately.

